# 6.5 Clinical laboratory tests

Safety laboratory determinations will include hematology, blood chemistry, liver function tests, and coagulation tests at the Screening visit (within 1 week prior to dosing), Cycle 1 Days 1 and 15, Day 1 of all subsequent cycles, the End of Treatment visit, and the 30-day Safety Follow-up visit. If clinically indicated, some or all of these tests may be repeated on other study days. All laboratory tests will be performed at a central laboratory designated by the Sponsor.

- Hematology: complete blood count (CBC) including hemoglobin, hematocrit, white blood cell count (WBC) with 5-part differential, red blood cell (RBC) count, and platelet count
- Blood chemistry: albumin, bicarbonate, blood urea nitrogen (BUN), calcium, chloride, creatinine, glucose, magnesium, phosphate, potassium, total protein, sodium, and uric acid
  - Creatinine clearance as calculated by the Cockcroft-Gault equation (at the Screening visit only)
  - 25-hydroxy vitamin D and 1,25-dihydroxy vitamin D (at C1D1, C3D1, C5D1, and the End of Treatment visit only),

- Liver function tests (LFT): ALT, AST, ALP, total and direct bilirubin, lactate dehydrogenase (LDH)
- Coagulation tests: prothrombin time (PT), INR, and partial prothrombin time (PTT) (at the Screening and End of Treatment visits and if clinically indicated)
- Serum pregnancy test: for women of child-producing potential at the Screening visit (within 72 hours prior to dosing), and End of Treatment visit. In addition, serum- or urine pregnancy testing will be performed monthly (on Day 1 of each treatment cycle) while the patient receives study treatment, at the 30-day Safety Follow-up visit, and monthly until 120 days after the last administration of study drug. Pregnancy testing after the End of Treatment may be performed at the patient's local gynecologist to reduce the burden related to study visits at the site, but must be communicated to the study investigator.

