# 7.3.2 Hyperphosphatemia

Because hyperphosphatemia is not defined by CTCAE v. 4.03, for the purpose of this protocol hyperphosphatemia is defined as:

- Grade 1: > ULN to < 7.0 mg/dL (< 2.26 mmol/L)
- Grade 2: Non-invasive intervention required (e.g., withhold drug or modify dose) orbetween 7.0 9.0 mg/dL (2.26 2.90 mmol/L)
- Grade 3: Severe or medically significant, but not immediately life threatening, or > 9.0 - 10.0 mg/dL (> 2.90 - 3.23 mmol/L)
- Grade 4: Life-threatening consequences, urgent intervention indicated e.g., dialysis or > 10.0 mg/dL (> 3.23 mmol/L)

Table 5 guides interventions for the management of hyperphosphatemia considered at least possibly related to derazantinib. For all patients, it is recommended to restrict phosphate intake to 600–800 mg daily.

Serum phosphate level	Action (For serum phosphate $\geq$ 7.0 mg/dL, consider adding an oral phosphate binding/reducing agent until serum phosphate level returns to < 5.6 mg/dL)
< 7.0 mg/dL (< 2.26 mmol/L)	Continue derazantinib at current dose.
7.0 – 9.0 mg/dL (2.26 – 2.90 mmol/L)	Withhold derazantinib with weekly reassessments until the level returns to $< 5.6 \text{ mg/dL}$ ; the patient may restart derazantinib at the dose prior to hyperphosphatemia. If hyperphosphatemia lasts $> 2$ weeks, consider restarting at the next lower dose.
> 9.0 – 10.0 mg/dL (> 2.90 – 3.23 mmol/L)	Withhold derazantinib with weekly reassessments until the level returns to $< 5.6$ mg/dL; the patient may restart at the next lower dose level.
> 10.0 mg/dL (> 3.23 mmol/L) or significant alteration from baseline renal function; or Grade 3 hypercalcemia	Withhold derazantinib with weekly reassessments until the level returns to $< 5.6$ mg/dL; the patient may restart at two dose levels lower, or permanently discontinue derazantinib (e.g., if considered life threatening event).

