#### 7.3.4 Management of QTc prolongation or other significant ECG abnormalities

If significant QTc prolongation and/or significant ventricular arrythmia is observed, i.e., a prolonged QTc interval  $\geq$  501 msec on at least two separate ECGs (consistent with a CTCAE v4.03 Grade 3 event), derazantinib must be withheld, and the patient must be monitored by the investigator and hourly (triplicate) 12-lead ECG obtained until the QTc has returned to  $\leq$  470 msec. The clinical context and possible factors contributing to QTc prolongations such as electrolyte abnormalities (potassium, calcium or magnesium), concomitant medications, or other clinical factors such as cardiac ischemia must be carefully assessed, and any findings documented in the eCRF. The decision to continue treatment with derazantinib should be reviewed and supported by a cardiologist.

Once QTc prolongation has resolved, and if a decision was made to continue treatment with derazantinib, patients may continue treatment at a lower dose with an ECG monitoring schedule defined by the cardiologist.

Patients who experience a QTc interval  $\geq$  501 msec on at least two separate ECGs after dose reduction will be discontinued from study.

All significant QTc prolongations or other relevant ECG abnormalities, will also be evaluated centrally.

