#### 3.1.2 Definition of Baseline

Assessment of change from baseline will include only those patients with both baseline and post-baseline measurements. The last evaluable/non-missing observation/assessment, including unscheduled visits taken before the first dose of study drug will be used as the baseline, unless otherwise specified.

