#### 3.1.3 Visit Windows

All data will be tabulated per the evaluation visit as recorded on the electronic case report form, even if the assessment is outside of the visit window. With the exception of the baseline definition, unless otherwise stated in the analysis sections below, unscheduled visits will only be included in data listings.

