#### 3.2.8.2 Laboratory Variables

Local laboratory results will only be listed.

Central laboratory results will be summarized with descriptive statistics at each scheduled time and for the change from baseline. Repeated or unscheduled tests will not be summarized for each scheduled visit (with the exception of baseline which may include unscheduled visits). Baseline values and values at each visit for each laboratory parameter collected be descriptively summarized and plotted over time using a boxplot.

Laboratory data will also be summarized using shift tables where appropriate. Each patient's continuous laboratory safety parameter values will be flagged as "low", "normal", "high" or "missing" relative to the normal ranges. Each patient's categorical laboratory safety parameter values will be flagged as "abnormal" or "normal". This categorical data will be summarized in shift tables comparing the minimum post-baseline value, maximum post-baseline value and all other relevant post-baseline visits with those at the baseline visit. Note that minimum post-baseline will only be displayed in the instances where there is a range with lower limit of normal (LLN) >0. For parameters that have gradings for both low and high values, low and high will be summarized separately.

In the shifts of low values, any high values will be classified as normal and the worst low grade will be summarized. And in the shifts of high values, any low values will be classified as normal and the worst high grade will be summarized.

In addition, CTCAE grade and hyperphosphatemia grade will be summarized. Shift tables of grade from baseline to maximum or minimum on-treatment as applicable will be produced.

Since hyperphosphatemia is not defined by CTCAE v. 4.03, as per protocol hyperphosphatemia is defined as:

Grade 1: > upper limit of normal (ULN) to < 7.0 mg/dL (<2.26 mmol/L)

Grade 2: Non-invasive intervention required (e.g., withhold drug or modify dose) or between 7.0 - 9.0 mg/dL (2.26 - 2.90 mmol/L)

Grade 3: Severe or medically significant, but not immediately life threatening, or > 9.0 - 10.0 mg/dL (> 2.90 - 3.23 mmol/L)

Grade 4: Life-threatening consequences, urgent intervention indicated e.g., dialysis, or > 10.0 mg/dL (> 3.23 mmol/L)

Central and local laboratory results will be included in by-patient listings and will include CTCAE grade and hyperphosphatemia grade at each visit, as well as change from baseline at each visit.

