# 3.2.8.4 Electrocardiogram (ECG)

The actual value and change from baseline to each visit and at end of study will be descriptively summarized by visit for ECG parameters (e.g., heart rate, RR interval, PR interval, QRS duration, QT interval, QTcF interval and QTcB interval). For all patients, a standard, triplicate, 12-lead ECG must be performed at all study visits using the pre-programmed device provided by the Sponsor. Summary tables will consider the mean of the triplicate measurements at each visit as the single reported value.

A categorical analysis of QTcF interval and QTcB interval correction will also be presented, based on the number and percentage of patients meeting or exceeding specific thresholds for absolute QTcF/QTcB interval prolongation and change from baseline in QTcF/QTcB interval. In this analysis, the mean of the triplicate measurements will not be used; instead, the maximum at each timepoint will be considered.

For absolute QTcF/QTcB interval prolongation, the number and percentage of patients within the following thresholds will be summarized at each visit. The worst (largest) value will also be summarized.

- Interval  $\leq 450 \text{ ms}$
- Interval >450 ms and  $\leq$ 480 ms
- Interval >480 ms and  $\leq$ 500 ms
- Interval >500 ms

The change from baseline in QTcF/QTcB interval to the worst (largest) post-baseline observation and at each study visit will also be summarized, considering the following thresholds:

- Interval increased from baseline  $\leq 30 \text{ ms}$
- Interval increased from baseline >30ms and  $\leq 60$  ms
- Interval increased from baseline >60 ms

For the analysis of change from baseline, the mean of the triplicate measurements will be used for baseline, but the maximum of triplicate measurements will be used for post-baseline values.

Local and central ECG data will be presented separately in the summary tables, and will be presented by timepoint. All ECG data will be provided in a by-patient listing.

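### The SAP's default sends unscheduled post-baseline tests to listings and never exempts its worst-value laboratory, Hy's law and QTc outputs, so these can understate severity

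*SAP*

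**What the plan says.** SAP 3.1.3 sets the default for all data. Apart from the baseline definition, "unless otherwise stated in the analysis sections below, unscheduled visits will only be included in data listings". SAP 3.1.2 supplies the one clear exception: the last evaluable value "including unscheduled visits taken before the first dose of study drug will be used as the baseline".

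SAP 3.2.8.2 keeps repeat and unscheduled laboratory tests out of the summaries by scheduled visit, again with baseline as the only exception. It then asks for worst-value outputs: "Shift tables of grade from baseline to maximum or minimum on-treatment as applicable will be produced". For local laboratories it says "Local laboratory results will only be listed". The Hy's law text counts patients above multiples of the upper limit of normal after baseline and plots peak values. SAP 3.2.8.4 classifies QTcF and QTcB at each visit and adds "The worst (largest) value will also be summarized". It presents local and central ECGs in separate tables.

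On the protocol side, section 6.5 schedules laboratory tests on Days 1 and 15 of Cycle 1, then on Day 1 of each 28-day cycle, at End of Treatment and at the 30-day follow-up. It adds: "If clinically indicated, some or all of these tests may be repeated on other study days". Table 5 in section 7.3.2 directs sites to "Withhold derazantinib with weekly reassessments until the level returns to" below 5.6 mg/dL. Section 7.3.4 requires, after a QTc of 501 msec or more on at least two ECGs, "hourly (triplicate) 12-lead ECG obtained until the QTc has returned to" 470 msec or less. Section 7.7.2 asks for liver tests every 4–5 days while hepatotoxic drugs are co-administered.

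**The concern.** A worst-value table is meant to show the most extreme result each patient had. If it is filled only from scheduled visits, it shows the most extreme result on days fixed in advance. From Cycle 2 those days come once every four weeks, while the tests done because something looked wrong fall between them. For example, a patient whose phosphate exceeds 9.0 mg/dL (protocol Grade 3) only at an unscheduled draw would appear in the shift table at a lower grade.

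The default is also asymmetric. An unscheduled value before the first dose can set the baseline, but by default an unscheduled value on treatment cannot set the post-baseline extreme.

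The outputs concerned describe risks that protocol 7.8 names: increased transaminases (important identified risk), hyperphosphatemia (important potential risk) and QT prolongation (potential risk).

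**Working it through.** The documents state no figure to reproduce. The check is a reading of the text, followed by an illustration.

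**1. Does any analysis section lift the default?**

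| Output | Values the SAP asks for | Statement that unscheduled post-baseline tests count |
|---|---|---|
| Low/normal/high shift tables (3.2.8.2) | Minimum and maximum post-baseline | None |
| CTCAE and hyperphosphatemia grade shifts (3.2.8.2) | Maximum or minimum on treatment | None |
| ALT, AST, bilirubin multiples and Hy's law (3.2.8.2) | Post-baseline; plots of peak values | None |
| QTcF/QTcB categories and change (3.2.8.4) | Largest value | None |

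Omission from these outputs therefore follows from the 3.1.3 default together with silence later on. No sentence excludes the tests from these particular tables.

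**2. How many tests fall off schedule?** Protocol 5.4 ties visits to Cycle 1 Day 1 regardless of drug holds, so the scheduled grid keeps running during a hold. In one 28-day cycle from Cycle 2:

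- Weekly phosphate: 28/7 = 4 draws, 1 scheduled, 3 unscheduled (75%).
- Liver tests every 4 days: 28/4 = 7 draws, 6 unscheduled (86%).
- Liver tests every 5 days (days 0, 5, 10, 15, 20, 25): 6 draws, 5 unscheduled (83%).
- Hourly ECGs: essentially all unscheduled after the first.

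These are shares of tests, not shares of peaks.

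**3. How often would scheduled visits miss an excursion?** Assume it starts at a random time and lasts d days. With visits every 28 days, P(missed) = 1 − d/28:

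- d = 7: 1 − 7/28 = 75%
- d = 14: 1 − 14/28 = 50%
- d = 21: 1 − 21/28 = 25%

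In Cycle 1 the spacing is 14 days, so a 7-day excursion is missed with probability 1 − 7/14 = 50%, and one of 14 days or more is not missed. Durations and random onset are assumptions; the documents give neither. An excursion missed by the grid affects the tables only if an unscheduled test found it, and that share is also not given.

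**4. Do the adverse event tables fill the gap?** They do not depend on visits. SAP 3.2.8.1 tabulates TEAEs by maximum grade and those leading to dose reduction or interruption, and lists transaminase elevations and hyperphosphatemia as events of special interest. QT prolongation is not on that list. All these tables rely on the investigator reporting the abnormality as an event. None of them combines transaminases with bilirubin, so none replaces the Hy's law summary.

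**The case against.** The strongest reply is that the default yields where a later section says otherwise, and that a request for the maximum, peak or largest post-baseline value is itself such a statement. The laboratory section restricts unscheduled tests only in by-visit summaries, and the ECG section sets the largest post-baseline observation beside the value at each visit. This reading is fair. It makes the SAP ambiguous rather than plainly exclusionary: two programmers could produce different tables from the same text. The same clarification settles either reading.

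Several stronger readings are tempting, and the documents do not support them:

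- A reader might infer that unscheduled values are kept out of every table. They are not: they can set baseline, and TEAE tables are unaffected. Local data are not wholly untabulated either, since local ECGs have their own tables.
- A reader might infer that the most abnormal values are the ones lost. The weekly phosphate and hourly ECG tests follow a triggering abnormality and run until recovery. If the trigger came at a scheduled visit, it is tabulated. A QTc of 501 msec already falls in the SAP's top absolute category (above 500 ms), so later hourly ECGs could not raise that category. The gap matters when the first or highest value came from an unscheduled test.
- A reader might infer that the protocol's toxicity rules create the local results that are only listed. Protocol 6.5 sends all laboratory tests to the central laboratory, so the local-results rule is a separate matter. The 4–5 day liver testing is a co-medication precaution, not a response to toxicity.
- A reader might take the 75% to 25% range as an estimate of understated severity. It is an illustration under assumed durations.

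The TEAE tables and graded listings do reduce the harm, but they do not remove it.

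**Conclusion.** The point holds in this form: under the plan as written, unscheduled post-baseline results go to listings by default, and nothing exempts the worst-grade, Hy's law or worst-QTc outputs. Those outputs can therefore omit off-schedule results and understate severity. That they do so in every case, or by a known amount, is not shown.

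The effect is confined to descriptive safety summaries. Neither primary endpoint nor any error rate is touched. The size depends on how long excursions last and how many are found only by unscheduled tests, and the documents give neither. The change is worth making because it removes a possible bias in reporting named risks at little cost.

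**What to change.** In SAP 3.1.3, 3.2.8.2 and 3.2.8.4:

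- Keep all by-visit summaries on scheduled visits, as now.
- State that every minimum, maximum, peak or worst post-baseline safety output uses all on-treatment central results, whether scheduled, unscheduled or repeat. Name the outputs: the laboratory shift tables, CTCAE and hyperphosphatemia grade shifts, ALT/AST/bilirubin thresholds and Hy's law, and worst QTcF/QTcB.
- Apply the same rule to unscheduled ECGs within the existing separate local and central ECG tables.
- Leave local laboratory results in listings, and flag there any local value that meets Hy's law or Grade 3 or higher criteria. SAP 3.2.8.2 already plans CTCAE and hyperphosphatemia grades in those listings. Pooling local values into the graded tables would be a separate and debatable choice and is not needed here.

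The cost is this clarifying text, a changed record filter for the named outputs and a flag in the listings. The downside is that some reported worst grades will become less favourable.

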### 3.2 STATISTICAL METHODS

### 3.2.1 Disposition of Patients and Analysis Populations

Patient disposition will be presented by substudy and overall. Tabulation will include the following:

- Number (%) of patients treated
- Number (%) of patients who discontinued treatment and primary reason for discontinuation of treatment
- Treatment phase duration (months)
  - Where the treatment phase duration will be calculated as the time from C1D1 to EOT visit. If EOT visit was not performed, then the last study visit prior to EOT will be analyzed.
- Number (%) of patients who performed the 30-day Safety Follow-up visit
- Number (%) of patients who entered Survival Follow-up, their last outcome at time of analysis (alive, continuing in follow-up, dead, lost to follow-up, alive, withdrawal of consent from study follow-up)
- Study duration (months)
  - Where the study duration will be calculated as the time from C1D1 to last survival follow-up date, or death. If last survival follow-up date, or death is missing, then the last date of contact will be analyzed.

The table will be based on the Safety/ITT Population.

The number and percentage of patients in each analysis populations (Safety/ITT, mITT, PP), including reasons for exclusion from each analysis population will be presented for all patients enrolled i.e. patients signed with informed consent.

The number of patients by country and site will be presented by the Safety/ITT population.

The following by-patient listings will be presented by substudy,

- Patient eligibility with inclusion and exclusion criteria details
- Patient enrollment
- Patient disposition
- Analysis populations
- IPDs

#### 3.2.2 Demographics and Baseline Characteristics

Demographic and baseline characteristics will be summarized by the Safety/ITT, mITT and PP populations.

The following variables will be listed and summarized in the demographic and baseline characteristic summary table using both continuous and categorical descriptive statistics.

- gender,
- race (White, Black or African American, Asian, American Indian or Alaska Native, Native Hawaiian or Other Pacific Islander, Other, not allowed to record per local regulation, unknown)
- ethnicity (Hispanic or Latino, not Hispanic or Latino, not reported),
- age (years) at baseline,
- baseline Eastern Cooperative Oncology Group (ECOG),
- baseline vital signs: height (cm), weight (kg), body mass index (BMI) (kg/m^2) calculated as weight (kg) / height (m)
- tumor's genomic status (FGFR2 fusion for Substudy 1, and FGFR2 mutations or amplification or

# Substudy 2)

Concordance of local FISH or NGS genomic testing compared to central FISH testing results will be summarized descriptively.

By patient listing of demographics, pregnancy test, tumor's genomic status will be produced,

# 3.2.3 Medical History (Non-Cancer Related)

Medical history will be coded using Medical Dictionary for Regulatory Activities (MedDRA) version 23.0 or later and will be summarized by system organ class (SOC) and preferred term (PT) for the Safety/ITT population. Patients will be counted only once for each SOC or PT in the event that they have multiple records of the same SOC or PT in the database. All medical history data will be listed.

# 3.2.4 Cancer-Related Medical History

Cancer-related medical history will be summarized for the Safety/ITT population. Descriptive statistics on cancer-related medical history will be presented for the following:

- Cancer history for iCCA
- Prior systemic cancer therapies
- Prior iCCA local therapies
- Prior iCCA cancer surgery/procedure
- Prior liver resection:
- Prior iCCA radiation therapies:

All cancer-related medical history data will be listed.

#### 3.2.5 Prior and Concomitant Medications, and Non-Drug Treatments/Procedures

Prior and concomitant medications will be summarized for the Safety/ITT population. All prior and concomitant medications will be included in by-patient data listings.

Non-drug treatments/procedures will only be listed for the Safety/ITT population.

Prior medication will be defined as any medication taken and stopped prior to the first dose of study drug. Concomitant medication will be defined as any medication ongoing at time of first dose of study drug or taken after the first dose of study drug.

Medications missing both start and stop dates, or having a start date prior to the first dose of study drug and missing the stop date, or having a stop date on or after the last dose of study drug and missing start date will be counted as concomitant.

For partial dates, the following approach will be taken:

• If the start day is missing but the start month and year are complete, a medication will be excluded as being concomitant only if the start month/year is before the month/year of study drug administration and if the stop date (either full date, month and year if missing day, or year if missing month and day) is before study drug administration.

• If the start day and month are missing but the start year is complete, a medication or procedure will be excluded as concomitant only if the start year is before the year of study drug administration and if the stop date (either: full date, month and year if missing day, or year if missing month and day) is before study drug administration.

Prior and concomitant medications will be coded using the WHO Drug Dictionary (WHODRUG Global B3 Sep2019 or above), and patient incidence will be tabulated by Anatomic Therapeutic Class (ATC) level 2, level 4 and PT. Patients will be counted only once for each ATC or PT in the event that they have multiple records of the same ATC or PT in the database.

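### SAP 3.2.5 defines concomitant medication by the first dose, but its missing-start rule uses the last dose and its partial-date rules do not let a known pre-dose stop date exclude a drug

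*SAP*

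**What the plan says.** Everything on this point is in SAP Section 3.2.5.

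- **Prior.** "Prior medication will be defined as any medication taken and stopped prior to the first dose of study drug".
- **Concomitant.** The definition covers "any medication ongoing at time of first dose of study drug or taken after the first dose of study drug".
- **Missing dates.** One sentence lists three cases that count as concomitant. The first two are "Medications missing both start and stop dates, or having a start date prior to the first dose of study drug and missing the stop date". The third is "or having a stop date on or after the last dose of study drug and missing start date will be counted as concomitant".
- **Partial start date, day missing.** A drug is ruled out "only if the start month/year is before the month/year of study drug administration and if the stop date". This second condition requires the drug to have ended before dosing.
- **Partial start date, day and month missing.** The rule has the same two-part form, with years compared in place of months.

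The same section tabulates prior and concomitant medications by ATC level and preferred term for the Safety/ITT population. It places every medication in by-patient listings.

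**The concern.** The definitions and the first two missing-date cases are consistent with a single cut at the first dose. The third case moves the cut to the last dose, and no reason is given. The result is odd: a record with both dates missing is expressly counted, while a record whose stop date shows use during treatment is not named.

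The partial-date rules fail in the other direction and for a different reason. They join two conditions with *and*, so a stop date known to precede dosing cannot exclude a drug by itself.

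What is at stake is the concomitant medication table. Protocol Section 10.3 names use of concomitant medications among the key safety parameters, and Protocol Section 7.7.2 lists drug classes to be avoided or used with caution. A reader of the safety results may turn to this table to see what patients took alongside derazantinib. It could omit some drugs taken on treatment and include some stopped before it.

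**Working it through.** The plan gives no figure to reproduce. The check sets each rule against the SAP's own definition.

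**Inputs**

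- First-dose definition, missing-start clause and partial-date rules: SAP 3.2.5.
- Treatment length: 1 to 8 months for most patients (SAP 1.1). Taking 30.4 days per month (assumption), 1, 4 and 8 months are 30, 122 and 243 days.
- Medications are reported if used within 30 days before first dose or during treatment (Protocol 6.1).
- Assumption: in the partial-date rules, study drug administration means the first dose.

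**A. Start date wholly missing, stop date known**

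Let F be the first dose date, L the last dose date, and T = L − F + 1 the days on treatment.

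- By the definition, the drug is concomitant if stop ≥ F.
- By the clause, it is named concomitant if stop ≥ L.
- Not covered by the clause: F ≤ stop ≤ L − 1, which is T − 1 days.

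| Treatment | T | Uncovered stop days (T − 1) |
|---|---|---|
| about 1 month | 30 | 29 |
| about 4 months | 122 | 121 |
| about 8 months | 243 | 242 |

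Example: first dose 1 March, last dose 30 June, start missing, stop 15 May. The definition makes this drug concomitant; the clause does not name it.

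The clause admits no drug stopped before dosing. With F in place of L, clause and definition agree on every stop date.

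**B. Start day missing, start month equal to dosing month**

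The start month is not before the dosing month, so the first condition fails and the drug cannot be excluded. With first dose on day d, the possible pre-dose stop dates in that month number d − 1.

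| First dose on day d | 1 | 5 | 10 | 20 | 30 |
|---|---|---|---|---|---|
| Pre-dose stop dates counted as concomitant | 0 | 4 | 9 | 19 | 29 |

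Example: first dose 25 March, start in March with day unknown, stop 10 March. This drug is prior by definition and concomitant by the rule.

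**C. Only the start year known, equal to dosing year**

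Take first dose on 20 June of a non-leap year as an illustration. Pre-dose stop dates in that year: 31 + 28 + 31 + 30 + 31 + 19 = 170. All are classed as concomitant, including all 30 in the reporting window before first dose. Because earlier medications need not be reported, 30 is the more realistic bound.

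These are counts of calendar dates, not of records or patients.

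**The case against.** The strongest reply concerns check A. A reader might infer that a drug with no start date counts only if it stopped on or after the last dose, so that drugs stopped on treatment necessarily drop out of the table. The documents do not support that. The missing-date sentence has no *only*; it is a list of inclusions, and records with both dates missing are also on it. The partial-date rules that follow do use *only if*, so exclusive wording was available. The definition just above already covers a drug known to have stopped after the first dose, and such a drug cannot be prior. Omission follows only if the programmer treats the clause as the operative test.

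This stands, and it limits the claim to a drug left uncovered that could be omitted. It does not remove the defect. If the definition settled every such case, the last-dose clause would be redundant, and a programmer looking for a rule on missing start dates will find that clause.

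The reply is weaker for checks B and C, where the rules misclassify when followed exactly. It is fair that they err towards inclusion, and that they do so only when the partial start falls in the dosing month or year.

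On consequences, three points hold:

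- SAP 3.1.4 expects complete dates, so affected records may be few.
- A patient counts once per ATC class or preferred term, so one misassigned record may leave the table unchanged.
- The SAP's Hy's law and ECG analyses (3.2.8.2 and 3.2.8.4) do not refer to the medication table, and Protocol 7.3.4 has contributing medications assessed patient by patient when QTc is prolonged.

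A reader might also infer that drugs to be avoided are the ones most likely to lack a start date or to be stopped on treatment. The documents give no data on either.

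**Conclusion.** Wrong as written, with minor impact. There are two separate faults, and the over-inclusion comes from the partial-date rules, not from the missing-start clause. Neither fault concerns drugs with complete dates.

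The effect is limited to descriptive medication tables. No efficacy endpoint, analysis population, test or error rate changes, and the listings still show every record. The documents give no rate of missing or partial dates, so the number of affected records cannot be derived. The day counts depend on the assumed month length and the illustrative dose dates; the conflict with the definition does not.

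**What to change.** 1. In the missing-start clause, replace *last dose* with *first dose*.
2. In both partial-date rules, make the stop date the only test: exclude a drug as concomitant if its known stop date, or the latest date that a partial stop date allows, is before the first dose; otherwise include it.

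The first change alone leaves the over-inclusion in place, so both are needed. The cost is a few lines of SAP text and a small programming change, with no new data collection.
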